5 PRIMARY, SECONDARY AND EXPLORATORY ENDPOINTS

5.1 **Primary Endpoint**

Sum of Pain Intensity Difference over 8 hours (SPID0-8)

5.2 Secondary Endpoints

- Sum of pain intensity differences from 0 to 2, 4, 6, 12 and 24 hours post-dose (SPID0-2, SPID0-4, SPID0-6, SPID6-12, SPID0-12, SPID12-16, SPID16-20, SPID12-24, SPID16-24, SPID0-24)
- Total pain relief from 0 to 2, 4, 6, 8, 12 and 24 hours post-doseTOTPAR0-2, TOTPAR0-4, TOTPAR0-6, TOTPAR 6-12, TOTPAR0-8 TOTPAR0-12, TOTPAR12-16, TOTPAR16-20, TOTPAR 12-24, TOTPAR16-24 and TOTPAR0-24)
- > Time to first use of rescue medication
- > Time and cumulative proportion of achieving complete pain relief
- > The cumulative proportion of participants taking rescue medication over the 24-hour period.
- Time to first perceptible relief measured by a stopwatch, time to meaningful relief measured by a stopwatch, and time to first perceptible relief confirmed by meaningful relief defined as the time to perceptible pain relief (the first stopwatch time) for those participants who had meaningful pain relief (the second stopwatch time)
- Pain Intensity Difference (PID) and Pain Relief scores at 0.5, 1, 1.5, 2, 3, 4, 5, 6, 7, 8, 9, 10, 11, 12, 14, (16, 18, 20 if awake), 22 and 24 hours post-dose
- Peak PID and peak pain relief
- Cumulative percent of participants with 'at least a 2-point PID' over time
- Global assessment of the investigational product
- Collect AE and clinical parameters

5.3 Exploratory Endpoints

> Not Applicable

6 ANALYSIS POPULATION AND TREATMENT GROUPS

6.1 Analysis Population

Randomized Population: All participants who received a randomization number, regardless of receiving study medication.

Safety Population: All participants who are randomized and take at least one dose of investigational product. Safety measures will be analyzed for all participants in the safety population.

Intent-To-Treat (ITT) Population:

All participants in the Safety Population. ITT population will be used as the primary analysis for the efficacy parameters.

Per Protocol (PP) Population: PP population will include all participants in ITT who do not have any major protocol violations and complete the 24-hour assessments. PP population will be used as secondary to conduct the sensitivity analysis for the selected parameters.

Major protocol deviations will be identified prior to database lock and may include but are not limited to significant violations of inclusion/exclusion criteria, noncompliance of the trial treatment taken, conditions such as vomiting and diarrhea or use of prohibited medications, and not following clinical trial protocol procedures. Any participant who rescues or vomits at or prior to 60 minutes after ingesting study medication will be excluded from the PP population.

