Participants would be encouraged not to sleep before midnight and if needed, woken for assessments (up to hour 14). Participants will be allowed a 6 hour rest period during the overnight hours of the 24-hour evaluation period and woken for the 22 hour assessment. The order of the pain assessments is Pain Intensity, then Pain Relief, then query about any AEs. At hour 24 or immediately prior to the first dose of rescue medication (if prior to hour 24), study participants will be asked to provide a Global Assessment of investigational product after completion of the other assessments. Additionally, participants will have vital signs taken after surgery, then at 1, 12 and 24 hours (+30 minutes post-surgery; +/-30 minutes from hours 1 through 24) post-dose.

Throughout the treatment period, the participants will be monitored for the occurrence of adverse events. Symptoms will be assessed by spontaneous reporting of AEs and by asking the participants to respond to a non-leading question such as "How do you feel?" or "Are you experiencing any other effects?" All reported or observed AEs will be collected and recorded on the case report form. The information will be based on signs and symptoms reported by the participant or observed by the study personnel staff during clinical evaluation.

Page 39 of 67

If a participant has any clinically significant, trial-related abnormalities at the conclusion of the treatment period, the clinical monitor (or designated representative) should be notified and the participant should be asked to remain at the trial site until such abnormalities are stabilized or resolve. If the participant is unable or unwilling to remain at the trial site, the clinical monitor (or designated representative) should be notified, and the Investigator should make every effort to arrange follow-up evaluations at appropriate intervals to document the course of the abnormalities.

Participants will be allowed the use of ice following the use of rescue medication. Ice will not be permitted for participants prior to randomization until after they have been administered rescue medication (if applicable). If participant has been administered rescue, ice will be given as requested by the participant for 20 minute increments. Upon completion of all trial procedures, participants will be discharged from the trial site. Participants will need to make prior arrangements for travel and should not drive themselves home.

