9.3 Populations for Analyses

For purposes of analysis, the following populations are defined:

Population	Description
Safety	All participants who are randomized and take at least one dose of investigational product. Safety measures will be analyzed for all participants in the safety population.
Intent-To-Treat (ITT)	All participants in the Safety Population. ITT population will be used as the primary analysis for the efficacy parameters.
Per Protocol (PP) Population	PP population will include all participants in ITT who do not have any major protocol violations and complete the 24 hour assessments. PP population will be used as secondary to conduct the sensitivity analysis for the selected parameters.
	Major protocol deviations will be identified prior to database lock and may include but are not limited to significant violations of inclusion/exclusion criteria, noncompliance of the trial treatment taken, conditions such as vomiting and diarrhea or use of prohibited medications, and not following clinical trial protocol procedures. Any participant who rescues or vomits at or prior to 60 minutes after ingesting study medication will be excluded from the PP population.

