3.1 Handling of Missing Data

3.1.1 Handling of Missing Data for Efficacy Assessments

Use of Rescue Medication:

In all analyses, for participants who take rescue medication, all pain intensity scores after intake of rescue medication will be imputed by the worse of the baseline or the score assessed immediately before taking rescue medication. All pain relief after intake of rescue medication will be imputed by "no relief" (0).

Missing data for efficacy parameter:

If Participants have missing pain data (i.e., pain intensity or pain relief scores) within the 24 hours period for the collection of pain rating data, but nonetheless complete the 24-hour period, then any missing timepoints will be replaced by a time-weighted average of the previous and the next available values (i.e., a linear interpolation for missing values) of the pain data (pain intensity / pain relief score). Intermittent missing data will only be imputed using linear interpolation method and if needed round down to the nearest whole number for pain relief scores, whereas for the categorical pain intensity the value will be rounded up to the nearest whole number.

Interpolation Formula,

$$y = \frac{y_2 - y_1}{x_2 - x_1} (x - x_1) + y_1$$

Where, and if needed round down to the nearest whole number for pain relief scores, whereas for the categorical paint intensity the value will be rounded up to the nearest whole number. y = missing pain data to be imputed, x = respective timepoint of y. y_1 and y_2 = pre and post available pain score of the missing pain data.

 x_1 and x_2 = respective timepoints of y_1 and y_2 .

If Participants do not complete the pain intensity/pain relief assessments for the full 24 hours, then the primary analysis will be calculated up to the last available timepoint, with no imputation for later timepoints.

In a sensitivity analysis, Participants who drop out of the study early because of a related AE or lack of efficacy will have later missing timepoints imputed using a worst-observation-carried-forward (WOCF) method, in which their worst observation at baseline or any time thereafter is imputed. For Participants dropping out early for any other reason, a last-observation-carried-forward (LOCF) imputation will be used.

No imputation will be done for missing data on stopwatch assessments of perceptible and meaningful pain relief. Instead, if data are missing for those assessments, data will be censored as described in Section 4.1.

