7.7 Efficacy Analysis

7.7.1 Primary Endpoint

The primary efficacy endpoint is the sum of change in pain intensity from 0 to 8 hours (SPID0-8). The treatment comparisons will be made in the following sequential order for SPID0-8 (each at 0.05 level of significance) in order to protect overall type 1 error at 0.05:

- Naproxen sodium/caffeine 220/65 mg versus Naproxen sodium 220 mg
- Naproxen sodium/caffeine 440/130 mg versus Naproxen sodium 220 mg
- Naproxen sodium/caffeine 220/65 mg versus Naproxen sodium/caffeine 440/130 mg

Once a comparison is statistically non-significant, the subsequent comparisons will be technically ineligible to be declared significant. However, all pairwise comparisons will be presented to provide a complete picture.

The primary efficacy endpoint is the summed pain intensity difference over 0 to 8 hours after Time 0 (SPID0-8). The formula for SPID0-8 calculation is presented in Section 4.1. The primary efficacy endpoint will be analyzed using an analysis of covariance (ANCOVA) model, which will include SPID0-8 as dependent variable, treatment as main effect and baseline pain intensity (Numerical Rating Score) as the covariate.

The least square (LS) mean, standard error (SE) and 95% confidence interval (CI) of LS mean for each treatment group will be reported.

In addition, the least square mean difference, SE, 95% Confidence interval of LS mean difference and p-value for all pairwise treatment group (include placebo) comparisons will be reported. Descriptive statistics (n, mean, SD, median, minimum, and maximum) for SPID0-8 will also be presented by treatment group.

ITT population (without imputation) will be used as the primary analysis for this primary endpoint while PP population (without imputation and single imputation) will be used as secondary analysis to conduct the sensitivity analysis.

In the primary analysis, endpoint will be imputed as described in Section 3.1.1, if any pain assessments are missing or Participant takes rescue medication.

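### The PP set for SPID0-8 requires 24 h completion, and SAP 3.1.1 gives no clear rule for a missed 0-8 h score when the participant leaves before 24 h

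*SAP*

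**What the plan says.** **Endpoint window.** SAP 5.1 names SPID0-8 as the primary endpoint. The formula in SAP 4.1 sums ten terms, for the scores at 0.5, 1, 1.5, 2, 3, 4, 5, 6, 7 and 8 h. Nothing after 8 h enters the sum.

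**PP set.** There is one PP definition for all parameters. SAP 6.1 admits ITT participants "who do not have any major protocol violations and complete the 24-hour assessments", and Protocol 9.3 sets the same condition. SAP 7.7.1 uses this set for the primary endpoint: "PP population (without imputation and single imputation) will be used as secondary analysis to conduct the sensitivity analysis".

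**ITT set.** ITT is everyone in the Safety Population (Protocol 9.3, SAP 6.1), with no 24 h condition. SAP 7.7.1 states: "ITT population (without imputation) will be used as the primary analysis for this primary endpoint". The same section then says that the endpoint in the primary analysis is imputed under Section 3.1.1 if assessments are missing or rescue is taken. The summary table in SAP 7.7.3 lists no imputation for ITT.

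**Missed scores.** SAP 3.1.1 introduces interpolation for participants with missing pain scores within 24 hours with the words "but nonetheless complete the 24-hour period, then any missing timepoints will be replaced by" a time-weighted average of the neighbouring values. The next sentence names linear interpolation as the only method for intermittent gaps and does not repeat the 24 h condition. For participants without the full 24 hours of assessments, the primary analysis runs to the last available timepoint and later timepoints are not imputed. A gap before that timepoint is not mentioned.

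**The concern.** Both rules tie an 8 h endpoint to what happens up to 16 h after its window closes.

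The PP analysis is the planned sensitivity check on the primary result. Removing people whose endpoint is fully observed, because of a later departure, makes it a less clean check. SAP 3.1.1 itself foresees early exits for a related adverse event or lack of efficacy, so such removals need not be unrelated to treatment.

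The interpolation rule could reach the ITT result, because SAP 7.7.1 applies Section 3.1.1 to the primary analysis. Take two participants with the same 0-8 h scores and the same missed score at 5 h. The one who stays to 24 h has a stated rule. The one who leaves at 20 h does not, and the choice falls to whoever programs the endpoint.

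**Working it through.** **The plan's own figure.** Inputs from Protocol 9.2 and SAP 2.3: difference 6.5, SD 16.9, power 90%, type I error 0.05, allocation 3:3:3:1:1, drop-out 5%. Sidedness is not stated; two-sided is assumed, since one-sided gives 116 per arm and does not fit.

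- n per arm = 2 × (1.960 + 1.282)² × 16.9² / 6.5² ≈ 142.1, so 143 (144 with the t distribution). The plan has 144.
- 3 × 144 + 2 × 48 = 528, and 528 / 0.95 = 555.8, so 556.

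The sample size is reproduced, and this point does not change it.

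**How many could leave PP with complete SPID0-8 data.** The documents do not say when drop-out falls relative to 8 h, so only a range can be given.

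- Lower end: all drop-out before 8 h gives 0.
- Upper end: all of the 5% after 8 h, with complete 0-8 h scores, gives 0.05 × 556 = 27.8, about 28. A large arm has 556 × 3/11 ≈ 152, of whom about 8 would be lost.
- At the earlier study's rate (Protocol 4.3: 193 randomized, 191 completed), 2/193 = 1.0%, and 556 × 2/193 ≈ 6 even if all left after 8 h.
- Power (two-sided, normal approximation) is about 0.918 at 152 per arm and 0.904 at 144, so regaining all of them changes little.

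**What a missed score does to one participant's SPID0-8.** The profiles are illustrative assumptions and interpolated values are left unrounded. The two right-hand columns are possible treatments of a non-completer, for whom no rule is stated.

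| PID profile, missed score | Interpolated (24 h completer) | Term left out | Next interval stretched over the gap |
|---|---|---|---|
| Constant 4, hour 5 missed | 32 | 28 | 32 |
| 0, 1, 2, 3, 4, 5, 5, 4, 3, 2, hour 5 missed | 25.5 | 21 | 25 |

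For the second row, the full sum is 0.5 × (0+1+2+3) + (4+5+5+4+3+2) = 26. Interpolation replaces the 5 at hour 5 by (5+4)/2 = 4.5, giving 25.5. Leaving the term out gives 26 − 5 = 21. Stretching lets the 6 h score of 4 cover two hours: 26 − 9 + 8 = 25. For these participants the handling moves the score by 0 to 4.5 points.

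**What that does to an arm mean.** If 5% of an arm had one such gap, left before 24 h and each lost 4 points, the mean would shift by 0.05 × 4 = 0.2 points, or 0.2/6.5 = 3% of the design difference. If both compared arms were affected alike, the shift would cancel in the difference.

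**The case against.** The strongest reply is that the primary analysis is barely touched. ITT has no 24 h condition, and complete 0-8 h data give the same ITT value whenever the participant leaves. This stands. A reader might infer that later events decide in general whether and how SPID0-8 is counted. The documents support that only for PP membership and, on one reading, for a participant who both misses a score inside 0-8 h and fails to complete 24 h.

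The interpolation limb is also contestable. The sentence on intermittent gaps carries no 24 h condition, and the non-completer rule bars imputation only at later timepoints, so a lenient reader would fill the earlier gap for everyone. If instead the no-imputation label governs ITT, neither participant is interpolated and the asymmetry goes. This also stands: the text is ambiguous, not a clear prohibition.

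Outcome-related departure may be rare, because participants are inpatients who must stay and be assessed regardless of rescue (Protocol 4.1, SAP 2.2). This limits the number affected but does not remove the rule.

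A reader might also infer that someone who sleeps through 16, 18 and 20 h is excluded from PP. The documents do not support that. Those assessments are scheduled only for participants who are awake, and Protocol 8.1.6 states: "Participants will be allowed a 6 hour rest period during the overnight hours". A sleeper has done everything required.

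Finally, PP sets specific to every window would be cumbersome with eleven SPID and eleven TOTPAR windows. That is fair, and the change below is confined to the 8 h endpoints.

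**Conclusion.** The point holds in two limited parts. First, the PP sensitivity analysis of SPID0-8 excludes participants whose endpoint is fully observed if they leave between 8 and 24 h; this is explicit in both documents. Second, SAP 3.1.1 leaves the handling of a 0-8 h gap unclear for anyone who does not reach 24 h, and the literal reading treats identical 0-8 h data differently.

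The size is small. The 28 of 556 is an upper bound that puts all assumed drop-out after 8 h. The 0.2-point shift assumes that 5% of an arm have such a gap and that the term is left out of the sum; under the stretched-interval reading the loss can be nil. It would be tempting to set a 4-point loss against the design difference of 6.5, but the first is one participant's score and the second a difference between arm means, so the ratio says nothing about the trial result. Sample size stands and power is nearly unchanged. This is a worthwhile clarification, not a threat to the primary conclusion.

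**What to change.** - **Protocol 9.3 and SAP 6.1:** for the PP analysis of SPID0-8 and TOTPAR0-8, require completion of the 0-8 h assessments instead of the 24 h assessments. The existing PP set can stay for the other windows.
- **SAP 3.1.1:** interpolate any missed score that has an observed or rescue-imputed score on both sides, whether or not the participant reaches 24 h.
- **SAP 7.7.1 and 7.7.3:** reconcile the no-imputation label for ITT with the statement that Section 3.1.1 applies to the primary analysis, so that it is clear which imputations the primary SPID0-8 contains.

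The cost is a few sentences in the SAP and a matching protocol clarification. The downside is that PP counts will differ slightly between the 8 h and later endpoints, so the disposition table in SAP 7.1 needs two PP counts.

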6.2 Treatment Groups

Treatment	Treatment Label for TLF				
Naproxen sodium/caffeine 220/65 mg	Group 1				
Naproxen sodium/caffeine 2 x 220/65 mg	Group 2				
Naproxen sodium 220 mg	Group 3				
Caffeine 100 mg	Group 4				
Placebo	Placebo				
Overall	Overall				

The below table includes the treatment labeling for all Tables, Listings and Figures (wherever as appropriate):

7 ANALYSES METHODS AND REPORTING DESCRIPTIONS

7.1 Participant Disposition

Participant disposition will be summarized using frequency count and percentage by treatment group and overall, for the randomized Participants:

- Number of Participants in the Randomized Population
- Number of Participants in the safety Population
- Number of Participants in the ITT Population
- Number of Participants in the Per-Protocol Population
- Number of Participants who Completed the Study
- Number of Participants who discontinued early from the study, as well as the reason for study discontinuation

Participants' disposition status will be listed by treatment group and will include Participant number, study completion status, Date of completion or discontinuation, and for those who discontinued early, specific reason for discontinuation (if reason of discontinuation is "Lost to follow-up" then "Date of last contact:" will be displayed.)

7.2 Demography and Baseline Characteristics

Demographic and baseline characteristics (including age, gender, race, ethnicity, childbearing potential, method of contraception, weight, height, BMI) will be summarized by treatment group and for the overall using descriptive statistics (n, mean, SD, median, minimum, and maximum) for Safety and ITT population. Demographic and baseline data will also be listed for safety population.

Dental X-ray examination, Surgical Trauma Rating and social history will be listed separately for safety population.

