8.1.3 Impaction Score

An Impaction Score will be used to assess each tooth based on the radiographic appearance and the intraoral examination. Each tooth will be rated from 1 to 4 using the following criteria: (1) erupted in tissue (2) soft tissue impaction (3) partial bony impaction, and (4) full bony impaction. Only participants whose mandibular impactions are scored (3) or (4) will be eligible to participate in the study.

Page 37 of 67

8.1.4 **During Surgery**

During surgery, participants will be administered a short acting local anesthetic (lidocaine or mepivacaine with or without vasoconstrictor) and nitrous oxide; at the discretion of the oral surgeon. Topical anesthetics may also be used prior to the administration of the short acting local anesthetic. Long duration local anesthetics like bupivacaine are not permitted. No other perioperative analgesic or anesthetic agents are permitted. Perioperative corticosteroids are not permitted.

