8.1.5 Surgical Trauma Score

At the completion of the procedure, the surgeon will rate the degree of surgical trauma on a of (1) mild, (2) moderate or (3) severe. Only individuals with a surgical trauma rating of mild (1) or moderate (2) will be eligible to participate in the study.

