2.3 Determination of Sample Size

Assuming that the treatment difference between the combo and naproxen alone of 6.5 and common standard deviation of 16.9 with respect to SPID0-8, a total of approximately 528 subjects (144 subjects per active treatment arm and 48 in the caffeine and placebo using a 3:3:3:1:1 ratio) are required to

achieve 90% of power with the type I error of 0.05, a total of approximately 556 subjects will be randomized into the study if a drop-out rate of 5% is assumed.

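### The SPID, TOTPAR and peak-score ANCOVAs adjust for baseline NRS alone; surgical trauma rating and mandibular impaction pattern, both known before randomisation, could be added and may recover a little precision

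*SAP*

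**What the plan says.** The primary model in SAP 7.7.1 has SPID0-8 as the outcome, with "treatment as main effect and baseline pain intensity (Numerical Rating Score) as the covariate". Protocol 9.4.1 specifies the same model. SAP 7.7.2 applies that method to the other SPID intervals and uses the same single covariate for TOTPAR, peak PID and peak pain relief.

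Two further baseline variables are collected and used to restrict entry:

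- **Impaction.** Protocol 8.1.1 makes the impaction score part of screening and requires the diagnosis of impaction before surgery. Protocol 8.1.3 adds: "Only participants whose mandibular impactions are scored (3) or (4) will be eligible to participate in the study". Each mandibular tooth is therefore partial or full bony, which gives three patterns: 0, 1 or 2 full-bony teeth.
- **Surgical trauma.** Protocol 8.1.5 has the surgeon rate trauma when the procedure ends, which is before pain qualification and randomisation in 8.1.6. It adds: "Only individuals with a surgical trauma rating of mild (1) or moderate (2) will be eligible to participate in the study".

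The only planned use of either is in SAP 7.2: "Dental X-ray examination, Surgical Trauma Rating and social history will be listed separately for safety population". The same section summarises age, height, contraception method and other characteristics by arm.

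**The concern.** Prespecified adjustment for a baseline variable that predicts the outcome reduces residual variance and removes the effect of chance imbalance in that variable. Trauma and impaction qualify on timing and completeness: treatment cannot affect them, and every properly enrolled participant should have both. They describe the surgical insult, whereas baseline NRS is a single rating at dosing that need not capture how pain develops over the next 8 hours.

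At stake is some precision in the SPID and TOTPAR comparisons. The first of these, FDC 220/65 mg against naproxen sodium 220 mg, opens a fixed sequence: if it is not significant, no later comparison can be declared significant. A second, smaller matter is that the planned tables will not show whether the arms are balanced on either variable. Randomisation is stratified on categorical pain only (Protocol 6.1.1). Whether that stratification factor belongs in the ANCOVA is a separate question.

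**Working it through.** **Inputs from SAP 2.3.** "Assuming that the treatment difference between the combo and naproxen alone of 6.5 and common standard deviation of 16.9 with respect to SPID0-8"; "achieve 90% of power with the type I error of 0.05"; "144 subjects per active treatment arm and 48 in the caffeine and placebo using a 3:3:3:1:1 ratio"; "a total of approximately 556 subjects will be randomized into the study if a drop-out rate of 5% is assumed". The plan does not say whether 16.9 is a raw or a baseline-adjusted SD. It is taken here as the SD remaining after baseline NRS.

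**Assumed input.** R² is the share of that remaining variance explained by trauma and impaction together. The documents give no value.

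**1. Reproduce the plan.**
- Normal approximation, two-sided: n per arm = 2 × (1.960 + 1.282)² × (16.9/6.5)² = 142.1, so 143. The exact t calculation gives 144.
- Power at 144 per arm is 90.4% (normal) or 90.2% (t, 286 df). One-sided testing at 0.05 would need only 116 per arm, so the plan is two-sided.
- Totals: 3 × 144 + 2 × 48 = 528, and 528/0.95 = 555.8, so 556. The plan's figures reproduce.

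**2. Degrees of freedom.** The planned ANCOVA has 528 − 5 arms − 1 covariate = 522 error df. Trauma costs 1 and a three-level impaction factor costs 2, which leaves 519.

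**3. Power after adjustment.** Residual SD = 16.9 × √(1 − R²); SE of the difference = SD × √(2/144); power from the noncentral t with noncentrality 6.5/SE and 519 df.

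| Assumed R² | Residual SD | SE | Power at 6.5 |
|---|---|---|---|
| 0 | 16.90 | 1.99 | 90.3% |
| 0.02 | 16.73 | 1.97 | 90.8% |
| 0.05 | 16.47 | 1.94 | 91.7% |
| 0.10 | 16.03 | 1.89 | 93.0% |

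**4. Break-even.** The error mean square falls only if (1 − R²)/519 < 1/522, that is, if R² exceeds 3/522 = 0.006.

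**5. What these R² values require.** For one two-level covariate with split p and a shift of b SPID0-8 points, R² = p(1 − p)b²/16.9².
- Even split, b = 6.5 (the whole assumed treatment effect): 0.25 × 42.25/285.61 = 0.037.
- Even split, b = 3.25: 0.009.
- 90/10 split, b = 3.25: 0.003, below break-even.
- Conversely, with an even split b = 2 × 16.9 × √R². An R² of 0.02 needs a shift of 4.8 points, 0.05 needs 7.6 and 0.10 needs 10.7.

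**6. Chance imbalance.** With an assumed even split, the SD of the difference in proportions between two arms of 144 is √(0.25 × 2/144) = 0.059, about 6 percentage points. The planned outputs would not tabulate a difference of that size.

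**The case against.** The strongest reply is that this is an optional refinement. The plan already prespecifies an adjusted analysis on the baseline value of the outcome scale, and it reaches its power target. No bias, contradiction or type I error problem arises. All of that stands.

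The reply goes further. Entry limits may show that the sponsor regards these variables as important, but they also narrow their range: severe trauma is excluded and each mandibular tooth scores 3 or 4. Protocol 4.2 chose the dental model partly because it is easily standardised in relatively homogeneous participants. Much of the control may already come from the design. This stands too, and it limits the likely gain.

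Nor is the change only a matter of SAP wording. Protocol 9.4.1 itself fixes the primary model, and SAP 7.13 declares no changes from the protocol. That is correct, and it raises the cost somewhat.

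Two stronger readings are tempting, and the documents support neither. A reader might infer that the plan is certainly losing precision; that requires a correlation with SPID0-8 beyond baseline NRS, and none is given. A reader might also infer that the matter is most serious for the 48-participant caffeine and placebo arms. However, all three comparisons in the type I error sequence are between 144-participant arms, and the power figures above apply only to those.

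None of this makes the adjustment wrong or harmful.

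**Conclusion.** The point holds as a small, optional improvement. The SPID, TOTPAR and peak-score models leave out two baseline variables that are fixed before randomisation and required for entry, and the plan may be giving up a little precision as a result. It is not an error, and the stated 90% power does not depend on it.

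The size is unknown and may be zero. A single evenly split covariate that shifts SPID0-8 by between half and all of the assumed treatment effect would add roughly 0.3 to 1 percentage point of power. The 93.0% at R² = 0.10 needs much stronger prediction than that. These figures rest on the assumed R², on 16.9 being the SD after baseline NRS, and on 144 evaluable participants per arm. The case for tabulating both variables by arm does not depend on R².

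**What to change.** Before unblinding:

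1. Prespecify trauma rating (mild/moderate) and number of full-bony mandibular impactions (0, 1 or 2) as covariates in the SPID, TOTPAR and peak-score ANCOVAs of SAP 7.7.1 and 7.7.2. Support this with an amendment to Protocol 9.4.1 or a declared change in SAP 7.13.
2. If the sponsor prefers to keep the protocol's primary model, place the same covariates in a named supportive ANCOVA.
3. In either case, tabulate both variables by arm in SAP 7.2 as well as listing them.

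The cost is the text changes, the amendment or declared departure, one additional table and 3 of 522 error degrees of freedom. No new data are needed.
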